5.6.3 Adverse Events

The AEs will be collected for each subject until 28 days after last study drug administration. The NCI CTCAE v5.0 will be used for AE grading.

The AE verbatim descriptions (investigator terms from the CRF) will be classified into standardized medical terminology using MedDRA. The AEs will be coded to the MedDRA (Version 22.1 or higher) lower level term closest to the verbatim term. The linked MedDRA PT and primary system organ class (SOC) are also captured in the database.

A TEAE is defined as the following:

- an AE that emerges during treatment (from first dose of study drug up to 28 days after last dose), having been absent at pretreatment (Baseline) or
- an AE that reemerges during treatment, having been present at pretreatment (Baseline) but stopped before treatment, or
- an AE that worsens in severity during treatment relative to the pretreatment state, when the AE is continuous.

The AEs will be summarized using the Safety Analysis Set. Only those AEs that are treatment-emergent will be included in summary tables. The incidence of TEAEs will be reported as the number (percentage) of subjects with TEAEs by SOC and PT. A subject will be counted only once within an SOC and PT, even if the subject experienced more than 1 TEAE within a specific SOC and PT. The number (percentage) of subjects with TEAEs will also be summarized by maximum CTCAE grade, or by relationship to study drug (Yes

Eisai Confidential Page 17 of 30

[means related to H3B-6545 or palbociclib or both] and No [means not related to either H3B-6545 or palbociclib]).

Number (percentage) of subjects will be summarized by treatment groups in the following analysis:

- Overview of TEAEs (including TEAEs, TEAEs by maximum grade, TEAEs by relationship, treatment-emergent SAEs, treatment-related TEAEs, TEAEs leading to study drug discontinuation, TEAEs with Grade ≥ 3, TEAEs leading to study drug reduction, TEAEs leading to study drug interruption, and TEAEs leading to death)
- TEAEs by SOC and PT
- TEAEs by SOC, PT and maximum grade
- TEAEs by PT in decreasing frequency
- TEAEs of Grade ≥3 by SOC and PT
- Treatment-related TEAEs by SOC and PT
- Treatment-related TEAEs by SOC, PT, and maximum grade
- Treatment-related TEAEs of Grade ≥3 by SOC and PT
- Treatment-emergent SAEs by SOC and PT
- Treatment-emergent SAEs by SOC, PT, and maximum grade
- Treatment related treatment-emergent SAEs by SOC and PT
- TEAEs leading to study drug discontinuation by SOC and PT
- TEAEs leading to death by SOC and PT
- TEAEs leading to study drug reduction by SOC, PT, and maximum grade
- TEAEs leading to study drug interruption by SOC, PT, and maximum grade Summary of death will be provided with number (percentage) of subjects who died during study treatment period or after study treatment. Details concerning subjects who died will be listed.

In addition, the following subject data listings will be presented:

- Listing of AEs associated with DLT
- Listing of AEs leading to discontinuation from study drug
- Listing of SAEs
- Listing of all AEs

Eisai Confidential Page 18 of 30

5.6.3.1 Grouping of AEs

Selected grouped terms will be defined by using coded terms, based on the MedDRA version used at the time of database lock. Grouped AEs will be summarized by treatment groups.

The grouped term "Bradycardia" is defined by PT of "Sinus bradycardia" and "Bradycardia". The QT prolongation will be summarized using standard MedDRA query (SMQ).

5.6.4 Laboratory Values

Laboratory results will be summarized by treatment groups on the Safety Analysis Set. The analysis will include assessment collected at baseline and/or during treatment (from first dose to 28 days after last dose date), using Système International (SI) units, as appropriate. Values that are non-missing and reported as 'below the detectable limit' of an assay will be replaced by half of the detectable limit in the summary tables.

For all quantitative parameters, the numeric value and the change from baseline to each post-baseline visit (including end of treatment visit and safety follow up visit) will be summarized by visit using descriptive statistics. Qualitative parameters summarized by frequencies (number and percentage of subjects) at each post-baseline visit (including end-of-treatment visit and safety follow up visit) will be reported.

Furthermore, the frequency of laboratory abnormalities by maximum post-baseline CTCAE grade will be summarized for selected laboratory parameters, including hemoglobin, White Blood Cell Count (WBC), Absolute neutrophil count (ANC), lymphocytes, platelet count, alkaline phosphatase (ALP), aspartate aminotransferase (AST), alanine aminotransferase (ALT), bilirubin, creatinine, estimated glomerular filtration rate (eGFR) calculated using the MDRD formula, thyroid stimulating hormone (TSH) and electrolytes. Shift tables will also be produced for selected parameters based on the baseline CTCAE grade and the maximum CTCAE grade at post-baseline visits.

Listings of laboratory results will be provided. In addition, a listing of potential Hy's law cases will be provided, including subjects who meets one of the following criteria at any post-baseline timepoint (not necessarily at the same timepoint): AST or ALT >3 x upper limit of normal (ULN). Parameters (AST, ALT, Total Bilirubin, ALP as multiples of ULN) at all timepoints will be included. Subjects meeting Hy's Law definition will be discussed in the clinical study report based on *FDA Guidance for Industry Drug Induced Liver Injury: Premarketing Clinical Evaluations* (2009).

5.6.5 Vital Signs

By-timepoint analysis: descriptive statistics for vital signs parameters (ie, systolic and diastolic blood pressure [BP], pulse/heart rate [HR], respiratory rate [RR], temperature and weight) during the treatment period and changes from baseline will be summarized by visit, presented by treatment groups on the Safety Analysis Set.

Eisai Confidential Page 19 of 30

Categorical analysis: the number (percentage) of subjects who meet the criterion (in Table 2 and Table 3) with at least 1 post-baseline result during the treatment period will be summarized (based on worst post-baseline results), and presented by treatment groups:

BP will also be summarized using a shift table from baseline to worst post-baseline by categories defined based on CTCAE grades.

Table 2 Blood Pressure Grades

Grade	Blood Pressure (mm Hg)		
	Systolic	Diastolic	
0 (Normal)	≤119	≤79	
1 (Prehypertension)	120 – 139	80 – 89	
2 (Stage 1 Hypertension)	140 - 159	90 – 99	
3 (Stage 2 Hypertension)	≥ 160	≥ 100	

For each subject at each visit, systolic blood pressure (SBP) and diastolic blood pressure (DBP) will be graded separately. Then the BP grade will be the worst of the 2 grades: SBP grade and the DBP grade. The worst BP category per subject during treatment will be used in the shift table.

Table 3 Criteria for Categorical Analysis of Vital Sign Parameters

Parameter	Criteria
Heart rate increase	Changes reflecting a more than 25% increase from baseline to a HR > 100 bpm
Heart rate decrease	Changes reflecting a more than 25% decrease from baseline to a HR < 50 bpm

bpm = beats per minute, HR = heart rate.

A listing of vital sign measurements will be provided.

5.6.6 Electrocardiograms

Central triplicate 12-lead ECG are collected at Screening, and on Day 1, Day 8, Day 15, Day 21 and Day 28 of Cycle 1, Day 1 of Cycle 2 or above, at the End of Treatment visit, or at the safety follow up visit. Local ECG may also be performed.

For each ECG parameter (QTcF, PR interval, etc), the average of triplicate at each timepoint (screening, predose and postdose at scheduled visits, end of treatment [EOT], unscheduled visits, etc) will be used in ECG analysis below:

• By-timepoint analysis: ECG parameters numerical results and changes from baseline at each scheduled timepoints (including EOT and safety follow up visit) during the treatment period will be summarized by treatment groups.

Eisai Confidential Page 20 of 30

• Categorical analysis: the number (percentage) of subjects who meet the following criterion with at least 1 post-baseline ECG result during the treatment period will be summarized (based on worst post-baseline results) and presented by treatment groups (Table 4):

Table 4 Criteria for Categorical Analysis of ECG Parameters

ECG parameter	Criteria		
QTcF	>450 and ≤480 msec		
	>480 and ≤500 msec		
	>500 msec		
	Change from baseline >30 and ≤60 msec		
	Change from baseline >60 msec		
	>500 msec or change from baseline >60 msec		
PR interval	Change-from-baseline >25% resulting in PR >200 msec		
QRS Change-from-baseline >25% resulting in QRS >120 msec			
HR	Changes reflecting a more than 25% decrease from baseline to a HR <50 bpm		
	Changes reflecting a more than 25% decrease from baseline to a HR <40 bpm		
	Changes reflecting a more than 25% increase from baseline to a HR >100 bpm		

ECG = electrocardiogram, HR = heart rate, QTcF = QT interval corrected for heart rate using Fridericia's formula.

Shift tables will present changes in ECG interpretation (categorized as normal; abnormal, not clinically significant; and abnormal, clinically significant) from baseline to worst post-baseline reading; if multiple interpretation records are collected in triplicate on Day 1 predose, the worst interpretation (eg, abnormal is worse than normal) prior to the first dose will be used as baseline interpretation.

All ECG data, including central and local 12-lead ECG data, will be listed. All ECG abnormalities based on central/local 12-lead ECG will also be listed.

5.6.7 Other Safety Analyses

5.6.7.1 ECOG PS

ECOG PS will be listed.

5.6.7.2 Other analyses

The following data will be listed:

- Multiple-gated acquisition (MUGA) or Echocardiogram (ECHO) for Left Ventricular Ejection Fraction (LVEF)
- Pregnancy test

Eisai Confidential Page 21 of 30

5.7 Other Analyses

Not applicable.

5.8 **Exploratory Analyses**

No exploratory analyses are planned for this study.

6 INTERIM ANALYSES

No formal interim analyses are planned. However, the cumulated safety and efficacy data by dose level will be reviewed periodically by the sponsors and investigators. The continuation of study enrollment will depend on the totality of the efficacy and safety data.

7 CHANGES IN THE PLANNED ANALYSES

If the SAP needs to be revised after the study starts, the sponsor will determine how the revision impacts the study and how the revision should be implemented. The details of the revision will be documented and described in the clinical study report.

Major changes of the analysis plan between SAP v1.0 to v2.0 are as follows:

- Specified new timing of primary analysis according to Protocol Amendment 04 (29 Aug 2022).
- Clarified summary of previous anti-cancer therapies and subgroup analysis
- Geometric mean (CV%) was deleted from the summary statistics for plasma concentrations of palbociclib and H3B-6545.
- The PK parameters calculated based on the terminal phase rate constant (λ_z) ($t_{1/2}$ and V_z/F) were deleted from the analysis plan, because the blood sampling time points were not enough to calculate λ_z accurately.
- Definitions and conventions for PK data handling were added.

8 DEFINITIONS AND CONVENTIONS FOR DATA HANDLING

Baseline is defined as the last non-missing pre-treatment value (or average value for ECG parameters, when multiple assessments are collected in triplicate at a timepoint) from either a scheduled or an unscheduled assessment.

Pre-treatment assessments: If both date and time are available, a pre-treatment assessment is defined as one that is measured before the date and time of the first dose of study drug. If only date is available and time is missing/not collected, scheduled assessment(s) measured on first dose date of study drug will be considered pre-treatment; unscheduled assessment measured on first dose date will be considered as post-treatment.

Eisai Confidential Page 22 of 30

On-treatment assessments (or assessments during treatment period) are defined as post-baseline assessments from first dose date of study drug to 28 days after the last dose of study drug. End of treatment assessments are those collected at the EOT visit. Safety follow up assessments are those collected at the safety follow up visit. On treatment assessments for end of treatment visit and safety follow up visit will be reported in 'by-timepoint' analysis and included in all abnormality/threshold analysis.

Study Day 1 is defined as the date of the first dose of study drug administered.

If there are multiple values reported for an assessment at a specific visit/timepoint, the average value will be calculated and used in summary tables and figures. Both original values and averages will be displayed in subject data listings.

All by-visit analyses will be performed using assessments at corresponding scheduled visits (including EOT and safety follow-up visits). A scheduled visit will be included in summary tables when there are $\geq 10\%$ subjects (based on number of subjects dosed) having non-missing assessment at the visit. For shift tables, all post-baseline assessments including those collected at scheduled and unscheduled visits will be used.

Pharmacokinetic assessments: The lower limit of quantification (LLOQ) in plasma is 1.00 ng/mL for palbociclib and 1.00 ng/mL for H3B-6545, respectively. While calculating PK parameters, below lower quantification (BLQ) values will be handled according to 302-104.01-MNL. When developing individual concentration-time profiles, BLQ values will be handled according to 302-104.01-MNL. The handling of anomalous concentration values will follow 302-104.01-MNL. When presenting individual/raw (raw, hereafter) values and summary statistics, the following rule will be applied for drug concentrations and PK parameters.

Typical variable	Unit	N	Digit rule	Raw Minimum Maximum	Mean Median	Standard deviation	Geometric Mean	CV (%)
Plasma concentration	ng/mL	X	Significant digits	3	3	3	_	ı
C _{max}	ng/mL	X	Significant digits	3	3	3	3	3
t _{max}	h	X	Fixed decimal places	2	2	ı	_	ı
AUC	ng•h/mL	X	Significant digits	3	3	3	3	3
CL/F	L/h	X	Significant digits	3	3	3	3	3
Ratio of exposure index	No units	X	Significant digits	3	3	3	3	3

Eisai Confidential Page 23 of 30

Individual pharmacokinetic data: The following data will not be included in the calculation of summary statistics.

- Plasma concentration data at predose if the blood samples are collected after administration
- PK data (plasma concentrations and PK parameters) in a patient with any dose modification (increase, reduction, or interruption) within 3 days prior to the blood sampling.
 - ie, The following PK data will not be included in the calculation of summary statistics;
 - PK data of palbociclib from a patient with dose modification in palbociclib from C1D5 to C1D8
 - PK data of palbociclib and H3B-6545 from a patient with dose modification in palbociclib or H3B-6545 from C1D18 to C1D21
 - PK data of H3B-6545 from a patient with dose modification in H3B-6545 from C1D25 to C1D28
- Dosing and sampling date/time are missing

The following case will be determined individually:

• Significant deviation from the allowance of PK blood sampling schedule

Further definitions and conventions for data handling will be presented in "Programming Specifications".

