Any other non- hematologic AE	Grade 4 Grade 3 (except diarrhea, rash, nausea, or vomiting lasting ≤72 hours) Any drug-related intolerable Grade 2 toxicity (other than hematological AEs) leading to administration of <75% of the dose during the DLT observation period

AE = adverse event; ALT = alanine aminotransferase; ANC = absolute neutrophil count; AST = aspartate aminotransferase; CTCAE = Common Terminology Criteria for Adverse Events; DLT = dose-limiting toxicity; GM-CSF = granulocyte–macrophage colony-stimulating factor; ULN = upper limit of normal.

a. Laboratory values that meet criteria listed in this table should be repeated and confirmed within 24 hours of the initial results being reported.

Intrasubject dose escalation: Once a subject has completed Cycle 3 at her assigned dose level of drug, intrasubject dose escalation will be allowed. No more than 2 dose escalations are allowed for any subject. Only subjects whose conditions have not progressed on treatment and did not have a dose reduction of either palbociclib or H3B-6545 because of AEs can escalate to the highest dose level that has completed DLT assessment and has been shown to be safe (no more than 1 DLT in 6 subjects). Subjects on the intrasubject dose escalation will *not* be included in the DLT analysis at the higher dose level.

Dose expansion: An additional 12 subjects will be treated at the MTD/RP2D to further characterize safety, tolerability, and PK and to provide preliminary estimates of efficacy. In Cycle 1, subjects will receive palbociclib PO QD on Days 1 to 21 and H3B-6545 PO QD on Days 9 to 28. In all subsequent cycles, palbociclib will be administered on Days 1 through to 21 and H3B-6545 will be administered Days 1 through to 28.

AEs will be managed by treatment interruption, dose reduction, and/or treatment discontinuation in accordance with the dose modification instructions outlined in the protocol. Treatment will continue until disease progression, development of unacceptable toxicity, or withdrawal of consent.

The data cutoff date for the primary analysis will be approximately 6 months after the last subject receives their first dose of study treatment. The end of study will be the last assessment for the last subject (eg, the last assessment for the last subject in the Extension Phase).

An overview of the study design and the decision rules for selection of the RP2D is presented in Figure 1.

Figure 1 Study Design and Selection of the Recommended Phase 2 Dose

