9.6.1.4.4 VITAL SIGNS AND WEIGHT MEASUREMENTS

Vital sign measurements (ie, resting heart rate, BP, respiratory rate, oral temperature) and weight (kg) will be obtained at the visits designated in the Schedule of Procedures/Assessments (Table 8) by a validated method. Blood pressure and pulse will be measured after the subject has been resting for 10 minutes. All BP measurements should be performed on the same arm, preferably by the same person. For subjects with an elevated BP (\geq 140/90 mmHg), confirmation should be obtained by performing 3 measurements (at least 5 minutes apart) to yield a mean value. Systolic BP \geq 160 mmHg or diastolic BP \geq 100 mmHg should be confirmed by repeat measurements after 1 hour.

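### SAP Section 8 averages repeat values within a visit and does not exempt worst-value tables, so the laboratory maximum-grade table and the worst-result vital-sign table can understate severity

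*SAP*

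**What the plan says.** **Averaging (SAP 8).** The rule opens "If there are multiple values reported for an assessment at a specific visit/timepoint" and continues that "the average value will be calculated and used in summary tables and figures". It adds: "Both original values and averages will be displayed in subject data listings". In the same section, the definition of baseline allows an average for ECG parameters only.

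**Shift tables (SAP 8, next paragraph).** "For shift tables, all post-baseline assessments including those collected at scheduled and unscheduled visits will be used".

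**Worst-value outputs.** For laboratory data, SAP 5.6.4 plans that "the frequency of laboratory abnormalities by maximum post-baseline CTCAE grade will be summarized for selected laboratory parameters", with separate shift tables of baseline against maximum grade. For vital signs, SAP 5.6.5 plans a categorical table built on each subject's worst result, using the criteria in SAP Tables 2 and 3. It also plans a blood-pressure shift table: "The worst BP category per subject during treatment will be used in the shift table". Neither section says whether individual values or visit averages are graded. SAP 5.6.6, by contrast, says plainly that ECG triplicates are averaged at each timepoint.

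**Repeats (Protocol).** Table 4, footnote a, in 9.1 reads "Laboratory values that meet criteria listed in this table should be repeated and confirmed within 24 hours of the initial results being reported". The same footnote stands under Table 5 in 9.5, so repeats are not confined to the DLT window. In 9.6.1.4.4, a pressure of 140/90 mmHg or more calls for three readings from which a mean is taken. A systolic value of at least 160 or a diastolic value of at least 100 "should be confirmed by repeat measurements after 1 hour". The protocol does not say whether a repeat is recorded under the same visit or timepoint as the value that prompted it.

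**The concern.** A table of maximum grade or worst result exists to show how bad a value became. The protocol asks for a second measurement when the first is extreme, and the second will often be milder. If both sit under one visit label and are averaged before grading, the subjects with the most extreme first values are those whose grade may fall. The blood-pressure trigger for the 1-hour repeat is also the lower limit of Grade 3 in SAP Table 2, so every reading in the top category should have a repeat.

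The tabulated grade would then depend on how a site labels the repeat: same visit and it is averaged, unscheduled and it may not be. Safety and tolerability are the primary objective and cohorts are small, so the laboratory and vital-sign tables should not depend on a data-entry choice.

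**Working it through.** The plan states no figure on this point, so there is none to reproduce. The check compares two orders of operation: grade each value and take the worst, or average first and then grade.

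**Inputs.** Grade 4 platelets below 25.0 ×10^9/L and Grade 3 from 25.0 to 50.0 (Protocol Table 4). Systolic Grade 3 at 160 mmHg or more and Grade 2 from 140 to 159 (SAP Table 2). Six DLT-evaluable subjects per cohort (Protocol 9.1). The paired values below are assumed.

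**Step 1, direction.** A mean is never more extreme than its most extreme component. Averaging can leave the worst grade unchanged or lower it; it cannot raise it.

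**Step 2, break-even with one repeat.**
- Upper cut-off T, first value T + d, repeat r: the mean is below T when (T + d + r)/2 < T, that is, r < T − d.
- Platelets, first value 25 − d: the mean reaches 25 or more when r ≥ 25 + d.

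If the repeat is also beyond the cut-off, the mean is too. A downgrade needs a repeat that misses the cut-off by at least about as much as the first value passed it.

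**Step 3, examples.** The first systolic value is taken to be the protocol's three-reading mean and the second the 1-hour repeat.

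| Assumed values | Mean | Worst individual grade | Grade of the mean |
|---|---|---|---|
| Platelets 22, 32 | (22 + 32)/2 = 27 | 4 | 3 |
| Platelets 22, 30 | (22 + 30)/2 = 26 | 4 | 3 |
| Platelets 20, 28 | (20 + 28)/2 = 24 | 4 | 4 |
| Systolic 164, 150 | (164 + 150)/2 = 157 | 3 | 2 |
| Systolic 165, 158 | (165 + 158)/2 = 161.5 | 3 | 3 |
| Systolic 180, 150 | (180 + 150)/2 = 165 | 3 | 3 |

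**Step 4, which outputs are exposed.**
- Laboratory frequency table by maximum grade: a summary table and not a shift table, so only the averaging rule speaks to it. Exposed.
- Categorical vital-sign table: the same reasoning. Exposed for the blood-pressure grades, where the protocol orders repeats.
- Laboratory and blood-pressure shift tables: the sentence on using all assessments brings in unscheduled visits but does not say that values within one visit stay separate. Ambiguous.
- ECG categories: averaging triplicates is the stated intention. Not at issue.

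**Step 5, an assumed range for systolic pressure.** The documents give no variability. Suppose true values are normal with SD 12 mmHg, there is one first reading and one repeat under the same label, and measurement SD is 4 to 12 mmHg. The simulated share of first readings of 160 or more whose average falls below 160 is:

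| True mean | SD 4 | SD 8 | SD 12 |
|---|---|---|---|
| 130 | 31% | 54% | 62% |
| 140 | 22% | 38% | 46% |
| 150 | 14% | 24% | 30% |

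This treats the first value as a single reading. Using the three-reading mean would make it less variable. The table shows only that downgrading need not be rare once the conditions are met.

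**Step 6, scale.** One subject is 1/6 = 16.7 percentage points in a cohort of six, and 1/24 = 4.2 to 1/12 = 8.3 points over an escalation part of 12 to 24. These are the weight of one subject, not an expected error.

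**The case against.** **Specific text should govern.** SAP 5.6.4 and 5.6.5 ask for the maximum and the worst, and a general convention need not override them. SAP Sections 8 and 9 also leave further conventions to programming documents, which are not among those reviewed. This is fair as a guess at intent. But the maximum of visit averages is still a maximum, and the averaging rule names summary tables without qualification.

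**Repeats may be separate timepoints.** A next-day laboratory repeat may well be logged as unscheduled, and a 1-hour repeat could have its own timepoint. This stands, and it is why the grade can be understated, not that it is. The label is left open.

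**A lone extreme value perhaps should not count.** Every downgrade requires a repeat that did not confirm the first value, and the protocol asks for confirmation. This is the strongest point. Averaging is not a confirmation rule, however. Platelets of 20 then 28 are not confirmed below 25, yet the mean stays Grade 4; 22 then 30 are equally unconfirmed and drop to Grade 3. If only confirmed values are wanted, the SAP should say so.

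**Stronger readings the documents do not support.**
- A reader might infer that all worst-value tables are affected. The shift-table sentence in the same section prevents that conclusion.
- A reader might infer that dose decisions are distorted or that tables will contradict the DLT listing. Nothing applies averaging to DLT determination, and an unconfirmed value may never be listed as a DLT.
- A reader might apply the argument to the hepatic DLT limit of 8 × ULN. No SAP table uses it as a cut-off.
- For pressures of 140/90 or more, the three-reading mean is the protocol's own instruction, so averaging those readings is not a fault.

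**Conclusion.** The concern holds in a limited form and should be fixed. Section 8, followed literally, can lower the worst grade in the laboratory maximum-grade frequency table and in the blood-pressure part of the categorical vital-sign table, and leaves the shift tables unclear. It cannot raise a grade, so any bias is toward a milder safety picture.

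The conclusion rests on two conditions that the documents do not settle: that the repeat shares the visit or timepoint label, and that it misses the cut-off by enough to carry the mean back across it. How often both occur is unknown. The 14% to 62% range for systolic pressure depends entirely on assumed means and SDs.

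The consequence is bounded. No passage applies the rule to DLT determination. Adverse-event grades are reported by the investigator (Protocol 9.6.1.4.1), and listings keep the original values. That is only a partial backstop: whether an isolated laboratory abnormality becomes an adverse event is left to the investigator's judgement, so the laboratory table should stand on its own.

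**What to change.** Amend SAP Section 8 to say:

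- Averaging applies only to by-visit descriptive statistics, to ECG triplicates at a timepoint, and to the protocol-defined mean of three blood-pressure readings. That mean counts as one value, and the 1-hour repeat is graded separately.
- Maximum-grade, shift and threshold tables grade each individual post-baseline laboratory or vital-sign value, including repeats and unscheduled values, and take the worst per subject.

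The ECG analysis in SAP 5.6.6 is unchanged.

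The cost is a sentence or two in the SAP and matching derivation rules. Some tabulated grades will be less favourable, and extreme values that a repeat did not confirm will be counted; a table footnote can say so.
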